1.2 BACKGROUND ON SATRALIZUMAB

Satralizumab (RO5333787; ENSPRYNG®) is a humanized anti-human IL-6R blocking monoclonal antibody that was designed by application of recycling antibody technology.

Antibody engineering techniques were utilized to give satralizumab pH-dependent binding affinity to IL-6R so that it binds to IL-6R under neutral conditions in plasma but dissociates under the slightly acidic conditions in endosomes, and is recycled to the plasma instead of being degraded in lysosomes, resulting in a longer plasma half-life. In addition, satralizumab is a modified IgG2 isotype, which reduces Fc-mediated effector functions.

The Clinical Development Program of satralizumab in NMOSD currently consists of two ongoing pivotal placebo-controlled, randomized, double-blind Phase III studies: Study BN40898 in adult and adolescent patients treated with 120 mg subcutaneous (SC) satralizumab in addition to background immunosuppressive therapy (IST) and Study BN40900 in adult patients treated with 120 mg SC satralizumab as a monotherapy. Both studies are ongoing in their open-label extension (OLE) periods.

Data from the completed double-blind periods of the pivotal Phase III Studies BN40898 (Yamamura et al. 2019) and BN40900 (Traboulsee et al. 2020) in adult and adolescents with NMOSD demonstrated a substantial magnitude of clinical benefit. Treatment with satralizumab led to significant reductions in the risk of protocol-defined relapse of 62% in

Study BN40898 (hazard ratio [HR]=0.38; 95% CI: 0.16 to 0.88) and 55% in Study BN40900 (HR=0.45; 95% CI: 0.23 to 0.89) compared with placebo.

Benefit was evident across multiple subgroups and was particularly high in the subgroup of patients who were AQP4-IgG seropositive, with risk reductions of 79% (HR=0.21; 95% CI: 0.058 to 0.750; p=0.0086) and 74% (HR=0.26; 95% CI: 0.108 to 0.627; p=0.0014) in Studies BN40898 and BN40900, respectively. Evidence of benefit in the subgroup of patients who were AQP4-IgG seronegative was inconclusive.

Based on the results of the studies summarized above, satralizumab (ENSPRYNG) has been approved by multiple Health Authorities as monotherapy or in combination with IST for the treatment of NMOSD in adult and adolescent patients who are anti-AQP4 seropositive, and is currently under review by other Health Authorities worldwide.

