1.3 STUDY RATIONALE AND BENEFIT-RISK ASSESSMENT

Satralizumab has been developed for the treatment of NMOSD, a serious condition that has substantial impact on day-to-day functioning of patients. Satralizumab has demonstrated a positive benefit/risk profile in the treatment of NMOSD in adult and adolescents patients who are AQP4 IgG seropositive.

The double-blind periods of both Study BN40898 and Study BN40900 have been completed (see summary of results in Section 1.2), and the studies remain ongoing in their OLE periods. Thus, patients ongoing in the OLE period can still benefit from the continuation of therapy with satralizumab in order to reduce the frequency and severity of NMOSD relapses.

Study WN42349 is an open-label, single-arm, rollover study of satralizumab that allows for patients ongoing in Study BN40898 and Study BN40900 to continue with long-term treatment with satralizumab for up to 3 years. The study aims to collect longitudinal safety and efficacy data. Analyzing the long-term safety and efficacy of satralizumab is of importance to help clinicians make informed decisions on the most appropriate therapy for their patients with NMOSD, a chronic disease requiring long-term maintenance relapse prevention therapy.

Although analysis of efficacy in the subgroup of patients who have AQP4-IgG seronegative NMOSD in Studies BN40898 and BN40900 was inconclusive, individual patients might benefit from continued treatment with satralizumab. Therefore, patients who were AQP4-IgG seronegative at screening in the pivotal studies may be enrolled in

this study, if the investigator considers continued treatment with satralizumab beneficial for the individual patient.

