6. STATISTICAL CONSIDERATIONS AND ANALYSIS PLAN

The purpose of this study is to assess safety and efficacy of long-term administration of satralizumab. Patients who are on treatment with satralizumab and ongoing in the OLE period of Study BN40898 or BN40900 can be enrolled in this study. For analysis

purposes, data of both parental studies and this study will be combined, where appropriate.

This section outlines the statistical analysis strategy and procedures for the study. A detailed methodology for statistical analyses of the data collected in this trial and the analyses in conjunction with the parental trials will be documented in a Statistical Analysis Plan (SAP).

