6.1 ANALYSIS POPULATIONS

6.1.1 Efficacy Analysis Populations

The intent-to-treat (ITT) population, which will serve as the primary population for the analysis of efficacy, consists of all randomized patients in the double-blind period of the parent Studies BN40898 and BN40900. The ITT population will encompass all patients from the parent studies, even if they do not participate in this study. Patients will be analyzed as randomized for analysis purposes in the ITT, even if patients randomized to placebo received satralizumab in the OLE period of the parent study.

In addition, all efficacy analyses will be conducted from the first dose of satralizumab in the parent studies. This analysis population is in line with the All-Patients-Treated (All satralizumab [ALLSA]) Population. Patients that were directly enrolled in the extension period of the parental studies will also be included in these analyses.

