6.5 EFFICACY ANALYSES

All efficacy analyses will be based on the ITT population and the ALLSA population. For both populations, data from Study WN42349 will be combined with data from the Studies BN40898 and BN40900.

All efficacy endpoints are secondary endpoints. The definitions are in line with Studies BN40898 and BN40900 to investigate long-term efficacy by summarizing the data of the parental studies and this Study WN42349.

Time to First Relapse

The time to first relapse (TFR) efficacy endpoint is based on several endpoint definitions to accommodate different estimand strategies. The most important intercurrent event is the use of therapy for the treatment of an acute NMOSD relapse (rescue therapy).

For the treatment policy strategy, the use of rescue therapy is ignored. Therefore, in the analysis for the treatment policy estimand the TFR is defined as the time from randomization in ITT or first dose of satralizumab in ALLSA to the first protocol-defined relapse as assessed by the investigator (iPDR).

The time point of relapse onset is defined as the time at which the patient experiences any new or worsening neurological symptoms representing NMOSD clinical relapse(s). For patients who have not relapsed at the time of analysis, the TFR will be censored at the clinical cutoff date (CCOD) or at time of withdrawal from study. There are no other censoring reasons.

For the composite strategy estimand, the use of rescue therapy (as defined in Section 4.4.1) for the treatment of acute relapses will be considered as an event in addition to the iPDR. Therefore, in the analysis for the composite estimand, the TFR is defined as the time from randomization in ITT or first dose of satralizumab in ALLSA to the iPDR or first use of rescue therapy, whatever comes first. Patients are either censored at the CCOD or at the time of withdrawal from study if they did not have an iPDR or did not receive rescue therapy. There are no other censoring reasons.

In addition, four further definitions of relapse are also analyzed:

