The ARR will be analyzed from randomization in ITT and from first dose of satralizumab in ALLSA. In both analyses the ARR is calculated as the total number of relapses experienced divided by the person-years of the whole study period. The unadjusted 95% CI will be presented based on the Poisson distribution.

For comparing the difference between the two treatment arms, negative binomial regression model will be used with ARR as response variable and treatment group, study ID of the parental study, and geographical region as covariates. In the ALLSA analyses, treatment group will not be included because all patients will receive satralizumab in this analysis.

In addition, the ARR by year of exposure will be estimated with use of a GEE Poisson regression model with repeated measurements and an unstructured covariance matrix, adjusted by Study Identifier of the parental study, and exposure year. Log-transformed patient years are included as an offset variable. In these analyses the overall ARR for the whole period is additionally estimated by a Poisson regression model. When comparing the difference between the randomized treatment arms of the parental studies, treatment is included as an additional covariate and the adjusted ARR and corresponding 95% CIs are presented for each arm and year.

All ARR analyses will be conducted for iPDRs, clinical relapses and treated clinical relapses.

Change in Expanded Disability Status Scale Score

The EDSS score will be assessed on scheduled visits during the study. The mean change in EDSS scores from randomization/first dose of satralizumab to every 24 weeks after the randomization/first dose of satralizumab visit will be analyzed.

Time to EDSS worsening based on the definition for PDR is estimated with a Cox regression with treatment group, and Study Identifier of the parental study as covariates. The HR and 95% CI for the treatment groups are estimated in this model, the p value is calculated on the basis of the stratified log rank test. In addition, Kaplan-Meier estimate of event-free rates will be provided for every 24 weeks and Kaplan-Meier curved will be estimated.

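### The plain Poisson 95% CI for the overall ARR is too narrow for inference beyond this cohort if patients' relapse rates differ markedly; a patient-level robust CI for the same estimate corrects this

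*Combined protocol and SAP*

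**What the plan says.** The Annualized Relapse Rate part of Section 6.5 defines the ARR as all relapses divided by all person-years, from randomization in ITT and from first satralizumab dose in ALLSA. For that crude rate it says: "The unadjusted 95% CI will be presented based on the Poisson distribution". Every relapse counts, so one patient can contribute several. The analyses are repeated for investigator-assessed protocol-defined relapses (iPDRs), clinical relapses and treated clinical relapses.

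The same section handles the other ARR analyses differently. To compare arms, a "negative binomial regression model will be used with ARR as response variable", with a version without treatment for ALLSA. The ARR by year of exposure uses a GEE Poisson model with repeated measurements. Alongside the latter, "the overall ARR for the whole period is additionally estimated by a Poisson regression model".

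Three other statements set the context:

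- **Populations.** Both are closed cohorts. Section 6.1.1 says: "The ITT population will encompass all patients from the parent studies, even if they do not participate in this study".
- **Purpose.** Section 1.3 says the long-term results should "help clinicians make informed decisions on the most appropriate therapy for their patients with NMOSD".
- **Status.** "All efficacy endpoints are secondary endpoints" (Section 6.5).

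**The concern.** A Poisson interval takes the variance of the relapse total to equal its mean. Suppose each patient has a personal relapse rate and these rates vary. A new sample of patients would then bring a new mix of rates, and the total would vary by more than Poisson. If the differences persist, the excess grows with follow-up, and long follow-up is the point of this study.

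The plan allows for extra-Poisson variation in the arm comparison and for repeated observations in the by-year ARR, but not in the interval for the crude overall ARR. In ALLSA there is no comparator, so that rate and its interval are a main summary of long-term relapse control. A clinician applying it to other patients could see more precision than the data support.

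Unequal rates are plausible from the documents, though not shown. Section 1.2 reports of the parent studies: "Benefit was evident across multiple subgroups and was particularly high in the subgroup of patients who were AQP4-IgG seropositive", with inconclusive evidence in seronegative patients. Section 6.5.1.1 records that prior ARR was a stratification factor in BN40898.

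**Working it through.** The documents give no ARR, interval width or dispersion, so there is no planned figure to reproduce. The check asks how the stated interval behaves over a range of assumptions.

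**Inputs.** From the documents: the estimator, the Poisson interval, the 95% level, and about 127 patients expected in this study. ITT and ALLSA also include parent-study patients who do not roll over, and their numbers are not given. Assumed: ARR 0.1 or 0.2; follow-up T uniform on 3 to 8 years; patient rates gamma-distributed with variance k times the squared mean and constant over time.

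**Scale for k.** Two equal halves with a 2-, 3- or 6-fold rate difference give k = 0.11, 0.25 or 0.51. For the 3-fold case, rates 1 and 3 have mean 2 and variance 1, so k = 1/4. A quarter of patients with a 3- or 6-fold higher rate gives k = 0.33 or 0.93.

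**Theory.** For a wider population, the true variance of log ARR divided by the Poisson variance is 1 + k × ARR × E[T²]/E[T]. Here E[T] = 5.5 and E[T²] = 5.5² + 25/12 = 32.33, so E[T²]/E[T] = 5.88. At k = 1 and ARR 0.2 the standard error should be larger by √(1 + 1 × 0.2 × 5.88) = 1.48. A nominal 95% interval then covers about 2Φ(1.96/1.48) − 1, or about 82%. The number of patients does not enter the factor.

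**Simulation.** 20,000 trials per setting, with counts Poisson(ARR × tᵢ × gᵢ). With D relapses in P person-years, two intervals for D/P were compared:

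- Exact Poisson: lower limit χ²(0.025; 2D)/(2P), upper limit χ²(0.975; 2D+2)/(2P).
- Patient-level robust: ARR × exp(±1.96 × SE), with SE = √[n/(n−1) × Σ(Yᵢ − ARR × Tᵢ)²]/D.

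Results for 127 patients, target the wider-population ARR, shown as ARR 0.1 / ARR 0.2:

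| k | Theoretical SE factor | Poisson coverage, % | Robust width ÷ Poisson width |
|---|---|---|---|
| 0 | 1.00 / 1.00 | 95.8 / 95.4 | 0.98 / 0.98 |
| 0.12 | 1.04 / 1.07 | 94.8 / 93.8 | 1.01 / 1.05 |
| 0.25 | 1.07 / 1.14 | 93.9 / 92.1 | 1.05 / 1.12 |
| 0.5 | 1.14 / 1.26 | 92.5 / 88.6 | 1.11 / 1.23 |
| 1 | 1.26 / 1.48 | 89.1 / 82.5 | 1.23 / 1.45 |
| 2 | 1.48 / 1.83 | 83.5 / 72.8 | 1.44 / 1.79 |

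The robust interval covers 94.0 to 95.0% in every row. With 170 patients the results are within 1 point.

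**Fixed-cohort reading.** Given these patients' own rates and follow-up, the total is a sum of independent Poisson counts and is itself Poisson. Simulated coverage of that target is 95.1 to 95.9% for k from 0.25 to 2, so on this reading there is no fault.

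**Length of follow-up.** At ARR 0.2 and 3 / 5 / 8 years, Poisson coverage is 93.9 / 92.9 / 90.8% at k = 0.25 and 88.2 / 85.1 / 78.7% at k = 1. If rate differences are redrawn every year (8,000 trials), there is no trend: 93.5 / 93.9 / 93.1% at k = 1.

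**Other follow-up assumptions.** With mean follow-up of 3, 5 or 7 years and the same two ARRs, Poisson coverage ranges over 87.4–94.0% at k = 0.5, 79.9–92.1% at k = 1 and 69.4–89.2% at k = 2. The robust interval covers 93.3–95.1% for k from 0 to 4.

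**The case against.** The best defence is that the interval is correct for the cohort the plan analyses. The wider target comes from one sentence of rationale, not from an endpoint or estimand. Entrants are also selected: they are on continuing treatment, and seronegative patients join only if the investigator sees benefit. A robust variance does not repair that. This stands as a limit on any generalization. It does not make the narrower interval suitable for the use that Section 1.3 describes.

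Second, the evidence for a large k is indirect. Hazard ratios by serostatus are relative effects, not on-treatment relapse rates. Prior ARR is history, and choosing a negative binomial model may be routine caution. This also stands: a 2-fold difference between halves costs about a point at most, and k = 2 lies beyond every worked example on the scale above. Rates may also be lower than assumed. At ARR 0.05, Poisson coverage is 95.1, 94.2, 92.6 and 90.0% for k = 0.25, 0.5, 1 and 2, and the robust interval is only 1.01 to 1.22 times as wide.

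Third, the ALLSA negative binomial model already allows for overdispersion. But it adjusts for study and region, so it estimates a different quantity, and nothing says that it replaces the interval for the crude rate.

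Fourth, Section 6 leaves "A detailed methodology for statistical analyses of the data collected in this trial" to a SAP. That can settle the variance used in the additional Poisson regression, which is not pressed here. The interval for the crude ARR, however, is already fixed in the protocol. Labelling it unadjusted does not tell readers that variation between patients is left out.

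**Conclusion.** The concern holds, with a stated condition. For inference to other patients, the plain Poisson interval loses little when rates differ mildly: 93.8 to 94.8% coverage at k = 0.12. The loss is material only when differences are marked and lasting: 82.5 to 89.1% at k = 1. These figures rest on an assumed ARR of 0.1 to 0.2, follow-up of 3 to 8 years and gamma-distributed rates; the loss shrinks at lower ARRs. For the fixed cohort the interval is valid.

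Only the stated precision of a secondary, descriptive estimate is affected. The ARR itself, the negative binomial arm comparison, the by-year GEE intervals, the Kaplan-Meier relapse-free rates and the primary safety analysis are untouched. The change is worth making because it costs almost nothing. Confidence is medium, because the dispersion is unknown.

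**What to change.** In Section 6.5 and the SAP, keep the crude ARR and take its 95% CI from a Poisson regression of each patient's relapse count, with log(patient-years) as offset and patient-level robust (sandwich) variance. Use an intercept-only model for ALLSA and a by-arm model for ITT. Apply this to iPDRs, clinical relapses and treated clinical relapses. The plain Poisson interval may stay if labelled as descriptive of this cohort only.

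A negative binomial interval is an acceptable alternative, with the relapse count as response and the same offset. It should be fitted without covariates or with a stated rule for averaging over study and region. Fitted without covariates, it covered 94.2 to 95.9% (2,000 fits per setting, k from 0 to 2). Its rate can differ from the crude ARR by about 5 to 6% at ARR 0.2 and k = 2, so the robust interval is preferred.

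The cost is wording only, with no new data. The interval becomes about 1.0 to 1.8 times as wide over the range studied and is essentially unchanged without overdispersion. There are two downsides. For the fixed cohort alone the robust interval is conservative (96.4 to 99.9% coverage for k from 0.25 to 2). In small arms (assumed 42 to 60 patients) its coverage falls to about 93% at k = 2.

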3.2 END OF STUDY AND LENGTH OF STUDY

The end of this study is defined as the date when the last patient, last visit (LPLV), occurs. The treatment period ends 3 years after the date the first patient enrolls in the study. The end of the study is expected to occur in second quarter of 2024.

In addition, the Sponsor may decide to terminate the study at any time.

The total length of the study, from enrollment of the first patient to the end of the study, is expected to be approximately 3 years and 3 months.

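### The negative binomial comparison of annualized relapse rates names the rate, not the relapse count, as response and states no follow-up offset

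*Combined protocol and SAP*

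**What the plan says.** The Annualized Relapse Rate part of Section 6.5 first defines the quantity: "In both analyses the ARR is calculated as the total number of relapses experienced divided by the person-years of the whole study period". Its next paragraph specifies the comparison of the two arms: a "negative binomial regression model will be used with ARR as response variable and treatment group, study ID of the parental study, and geographical region", the last three being the covariates. It gives no count response and no exposure term. In ALLSA the same model is used without treatment group.

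The paragraph after that describes a different model, a GEE Poisson regression of ARR by year of exposure. Only there does an exposure term appear: "Log-transformed patient years are included as an offset variable". The scope is wide: "All ARR analyses will be conducted for iPDRs, clinical relapses and treated clinical relapses".

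Three other statements bear on follow-up:
- Section 6.1.1, on who is in ITT: "The ITT population will encompass all patients from the parent studies, even if they do not participate in this study".
- Section 6.1.1, on switching in the parent study: "Patients will be analyzed as randomized for analysis purposes in the ITT, even if patients randomized to placebo received satralizumab in the OLE period".
- Section 3.2, on the end of treatment: "The treatment period ends 3 years after the date the first patient enrolls in the study".

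The opening of Section 6 defers detail to a statistical analysis plan. Nothing in the supplied text corrects the response variable.

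**The concern.** Dividing by follow-up breaks the mean-variance relation on which a negative binomial model rests. It also discards the information about how long each patient was observed: someone seen for six months counts as much as someone seen for seven years.

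Two things are at stake. The first is the reported interval for the arm comparison, which would reflect the mix of follow-up times rather than the information in the data. The second is agreement with the plan's own ARR. Placebo patients who switch to satralizumab stay in the placebo arm. Equal weighting therefore gives too much influence to short-stay patients who never switched, and the model's ratio moves away from the ratio of the pooled rates.

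The sentence also leaves a programmer to choose, because a patient-level ARR is never defined. Rates or counts, each with or without an offset, are four different analyses.

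**Working it through.** The plan gives no figure for this comparison, so there is none to reproduce. Arm sizes (90 and 80), relapse rates, dispersion k, follow-up and switch time below are all assumptions.

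**Variance.** For a patient with yearly rate μ followed t years, with gamma-Poisson counts, the observed rate has variance μ/t + kμ². The literal model assumes at least μ. When its fitted dispersion is zero, the ratio of model SE to true SE at equal follow-up is

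√[(1/μ) / (1/(μt) + k)].

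With μ = 0.15 and t = 5.5: 1/μ = 6.67 and 1/(μt) = 1.21. For k = 0.5, 1, 2, 3 the ratio is √(6.67/1.71) = 1.97, √(6.67/2.21) = 1.74, √(6.67/3.21) = 1.44 and √(6.67/4.21) = 1.26.

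**Example with switching.** Satralizumab 0.10/year; placebo 0.20/year for 1.5 years, then 0.10/year; 5.5 years in all.
- Placebo whole-period rate: (0.20×1.5 + 0.10×4)/5.5 = 0.127. Rate ratio: 0.10/0.127 = 0.786.
- Literal SE² is at least 1/(90×0.10) + 1/(80×0.127) = 0.209, so SE = 0.458.
- True SE² at k = 1: (1/0.55 + 1)/90 + (1/0.70 + 1)/80 = 0.0617, so SE = 0.248.
- SE ratio 1.84 (2.05, 1.57 and 1.39 at k = 0.5, 2 and 3).
- 95% CI: 0.32-1.93 literal, 0.48-1.28 with count and offset. Both include 1.

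**Simulation.** 1500 runs per cell, treatment as the only covariate, model-based SEs, two-sided 5% test. Null: 0.15/year in both arms. Power and expected ratio use the switching rates above. Ranges are over k = 0.5 to 3.

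| Follow-up | Literal SE / empirical SD (k = 0.5, 1, 2, 3) | Null rejection, literal | Variance, literal / offset | Power, literal vs offset | Expected ratio, literal vs pooled ARR |
|---|---|---|---|---|---|
| 5-6 years | 1.92, 1.76, 1.42, 1.27 | 0.000-0.007 | 1.0 | 0.001-0.018 vs 0.13-0.20 | 0.79 vs 0.79 |
| 5% leave in year 1, rest 3-8 years | 1.60, 1.47, 1.27, 1.14 | 0.003-0.017 | 1.1-1.4 | 0.018-0.043 vs 0.13-0.19 | 0.75 vs 0.78 |
| 25% leave in year 1 | 1.13, 1.06, 1.01, 0.92 | 0.035-0.067 | 1.6-2.4 | 0.10-0.13 vs 0.12-0.18 | 0.68 vs 0.77 |
| 40% leave within 1.5 years | 1.05, 1.00, 0.95, 0.88 | 0.040-0.071 | 1.6-2.5 | 0.15-0.17 vs 0.15-0.23 | 0.63 vs 0.75 |

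Count plus offset rejects 0.044-0.067 under the null throughout. The first row agrees with the closed form.

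**Drift of the ratio, by hand (25% leavers).** Take leavers at 0.5 year on average and the rest uniform on 3-8 years (mean 5.5).
- A stayer's placebo rate is 0.10 + 0.15/t, which averages 0.10 + 0.15×ln(8/3)/5 = 0.129.
- Equal weighting: 0.25×0.20 + 0.75×0.129 = 0.147; ratio 0.10/0.147 = 0.68.
- Pooled: (0.25×0.5×0.20 + 0.75×0.70)/(0.25×0.5 + 0.75×5.5) = 0.55/4.25 = 0.129; ratio 0.77.

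**Covariates.** With study (2 levels) and region (3 levels) in the model, k = 1, no treatment effect, 250 runs:
- 5-6 years: literal SE 0.380 against empirical 0.223, rejection 0.000; offset 0.223 against 0.219.
- 25% early leavers: literal SE 0.392 against 0.347, rejection 0.028; offset 0.252 against 0.251.

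**Separate check.** 80 per arm, 400 runs.
- All followed 6 years, null, k = 1: literal SE 0.413 against empirical 0.228 (ratio 1.81), rejection 0.0%.
- 30% early leavers, same null: rejection 1.8%, empirical SD 0.375 against 0.253 with offset.
- Constant rates, with follow-up unrelated to relapse risk: the median rate ratio stayed close to the truth.
- Partial repairs, with 45% and 20% early leavers in the two arms and no true difference: count without offset gave a ratio of 1.36 and 21.5% rejection; rate with offset gave a ratio of 0.73.

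**The case against.** The strongest reply is that the wording is shorthand. ARR is defined only as a pooled quantity and a negative binomial model is a count model, so naming ARR as response may just name the endpoint. The authors also know how to use an offset, since they state one for the GEE Poisson model. This may well be what is meant. But an offset stated for one model and not for its neighbour leaves the text ambiguous, and followed as written it gives the wrong analysis.

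Section 6 also says that "A detailed methodology for statistical analyses of the data collected in this trial and the analyses in conjunction with the parental trials" will be set out in a SAP. That is a fair place for the correction, but a general deferral does not change a response variable that has been named.

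Further points stand in part:
- The plan states neither a p value nor the type of SE for this model. Robust SEs would largely restore calibration, but not the lost precision.
- The largest distortions need near-uniform long follow-up, and there the error is conservative. With 25-40% early leavers, null rejection is close to nominal.
- Crossover dilutes both versions of the ratio, and the proposed sentence does not cure that. With 40% leavers, the literal 0.63 is nearer than the pooled 0.75 to the on-placebo contrast of 0.10/0.20 = 0.5. The point is only that the model should estimate the ARR the plan defines.
- Efficacy endpoints are secondary. The crude ARR with Poisson interval and the GEE Poisson analysis are unaffected.

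**Conclusion.** The point holds. Section 6.5 names a rate as the response of a count model and gives that model no offset. With model-based SEs, the literal SE is about 1.3 to 1.9 times the true one under near-uniform long follow-up. With 25-40% early leavers it is 0.88 to 1.13 times the true one, and the estimator's variance is 1.6 to 2.5 times that of count plus offset. At constant rates, with follow-up unrelated to risk and arm, the ratio is not materially biased; with switching and early leavers it departs from the pooled ARR ratio.

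The direction and size depend on the assumed rates, dispersion, follow-up and switch time. The correction will probably not turn an inconclusive comparison into a conclusive one: in the main switching scenarios (switch at 1.5 years) power with the offset was 0.12 to 0.23. With 5-6 years of follow-up it was 0.08-0.13 for a switch at 1.0 year and 0.21-0.41 for a switch at 2.5 years. What is at risk is a correct interval for a secondary endpoint under three relapse definitions, not the primary safety objective.

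**What to change.** In Section 6.5, and in any SAP text that follows it, replace the sentence on the between-arm model with wording such as: *Negative binomial regression of each patient's number of relapses, with log link and log(patient-years) as offset.* Keep the covariates as they are. Apply it in ITT, in ALLSA without treatment group, and for all three relapse definitions.

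Both parts must change together. Adding an offset while keeping ARR as response would correct for follow-up twice, and using the count without an offset would not correct for it at all.

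The cost is one sentence. Relapse counts and patient-years are already needed for the crude ARR and the GEE Poisson model, so no new data are required.
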